6.1 Dose Limiting Toxicities

DLT is defined as any hematologic or non-hematologic AE grade ≥3 with a suspected causal relationship to Plerixafor (including including ECG changes indicative of ischemia, ventricular tachycardia).

- Patients will be monitored for DLTs for 5 weeks from the start of the Plerixafor infusion.
- DLT's in the first cohort may occur before or after 14 days. If a DLT occurs in weeks 3 or 4 of treatment, we will treat next patient with a dose of 200 μg/kg/d x2 weeks. If a DLT occurs from the start of treatment through the second week of treatment, we will

Version #11, Date: 04-29-2015 Page 27 of 52

treat next patients at a dose of 100 μ g/kg/d x 4 weeks. If a patient experiences a DLT, the infusion will be discontinued. The next patient treated at the lower dose level as dictated by the mTPI table. If an early dose limiting toxicity occurs at lowest dose level (200 μ g/kg/d x 2 wk or 100 μ g/kg x 4wks) then the protocol will be stopped at that point.

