7.2 Adverse Event Reporting

Adverse events will be graded according to CTCAE v4.03. This is an off-label indication for plerixafor. Investigators will reference safety information to assess expectedness: IB. All adverse events except those clearly attributable to the underlying disease will be reported, including definitely, probably and possibly related. Both Serious and Non-Serious Adverse Events will be clearly noted in source documentation and listed on study specific Case Report Forms (CRFs). The Protocol Director (PD) or designee will assess each Adverse Event (AE) to determine whether it is unexpected according to the Informed Consent, Protocol Document, or Investigator's Brochure, and related to the investigation. All Serious Adverse Events (SAEs) will be tracked until resolution, or until 30 after the last dose of the study treatment.

SAEs CTCAE Grade 3 and above, and all subsequent follow-up reports will be reported to the Stanford Cancer Institute Data and Safety Monitoring Committee (DSMC) using the study specific CRF regardless of the event's relatedness to the investigation. Following review by the DSMC, events meeting the IRB definition of 'Unanticipated Problem' will be reported to the IRB using eProtocol within 10 working days of DSMC review, or within 5 working days for deaths or life-threatening experiences.

In addition, within 24 hours (US) or one business day (EU) of first knowledge of such serious
and related adverse event, we will notify Sanofi via fax, attention Sanofi Pharmacovigilance
(PV), or via email at:
Additionally, the Investigator will transmit to Sanofi PV an information copy of
any such report sent to the governing regulatory authority, prior to or at the time of authority
filing. The Investigator will make available to Sanofi promptly such records as may be necessary
and pertinent to investigate any such expedited adverse event, if specifically requested by Sanofi

Furthermore, the Investigator will inform Sanofi of the following:

- Any events that result in protocol amendments for safety reasons, as well as any safety related regulatory action such as a clinical hold of the Research;
- Any pregnancies occurring in patients who are exposed to the Product in connection with the Research. Please see section 10.2.1.3 for additional reporting guidance;

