11.2 Data and Safety Monitoring Plan

The Stanford Cancer Institute Data and Safety Monitoring Committee (DSMC) will be the monitoring entity for this study. The DSMC will audit study-related activities to determine whether the study has been conducted in accordance with the protocol, local standard operating procedures, FDA regulations, and Good Clinical Practice (GCP). This may include review of the following types of documents participating in the study: regulatory binders, case report forms, eligibility checklists, and source documents. In addition, the DSMC will regularly review serious adverse events and protocol deviations associated with the research to ensure the protection of human subjects. Results of the DSMC audit will be communicated to the IRB and the appropriate regulatory authorities at the time of continuing review, or in an expedited fashion, as needed.

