The prior is a beta with parameters 1 and 1 (roughly equivalent to two observations, one of these a DLT). Briefly, with the above settings, when the posterior probability falls below 0.25 (0.30-0.05), escalation to the next higher dose level is indicated; when the posterior probability falls above 0.35 (0.30+0.05), de-escalation is recommended; otherwise the next patient is to be treated at the same dose level. The rules for escalation and de-escalation for this design are contained in Table 12.1; they do not need to be modified during the course of the study. At the end of the study the toxicity data at all doses is combined using the "pool adjacent violators" algorithm to make toxicity probabilities non-decreasing; the maximum tolerated dose is calculated as the dose level that comes closest to the target toxicity level.

Table 12.1 show the action to be taken as each patient becomes evaluable for toxicity. It is used for all dose levels as follows:

- E means that the next patient is to be treated at the next higher dose. If the current dose is the highest planned $400 \mu g/kg/d \times 28 d$, the next patient is to be treated at the **same** dose level.
- S means that the next patient is to be treated at the same dose level. Note that a minimum of 3 subjects must be studied at a dose before escalation is indicated.
- D means that the next patient is to be treated at the next lower dose. If the current dose is the

- lowest planned 200 µg/kg/d x 14 d, the next patient is to be treated at the same dose level.
- U means that the current dose level is too toxic. No further patients are to be treated at this or at any higher dose level. If the current dose level is the lowest planned (200 μ g/kg/d x 2 wks total dose) no further patients will be treated. If the current dose level is not the lowest planned, the next patient should be studied at the next lowest dose (100 μ g/kg/d x 4 wks).

These definitions are in accord with our reading of the code used to produce the simulations which validated the mTPI design.

Toxicity will be monitored in the expansion phase at each increment of 5 patients. If DLT is observed in one out of the first 5 patients, or 2 of the first 10, or 2 of the first 15, toxicity will be reviewed to assess whether the trial should continue. This stopping rule has a 5% chance of being triggered if the true DLT toxicity rate is 5%, it has a 62% chance of being triggered if the true DLT rate is 30%.

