12.7 Criteria for future studies

This is a pilot study with the expectation that no more than 50% of patients will have stable disease at 6 months (defined as stable MRI and clinical status, including being on a stable dose of steroids and not on bevacizumab). We will therefore consider this regimen of interest if significantly more than 50% of patients achieve this benchmark and would move further to future studies should this benchmark be reached.

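### The Phase II DLT trigger names no reviewer, non-serious DLTs need not reach the DSMC, and the criterion for further study leaves toxicity out

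*Combined protocol and SAP*

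**What the plan says.** All references are to the combined protocol and SAP.

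- **The trigger (12.1).** Toxicity in the expansion phase is looked at in steps of five. The limits are one DLT among the first five, two among the first ten, and "2 of the first 15, toxicity will be reviewed to assess whether the trial should continue". No reviewing person or body is named. The section adds "This stopping rule has a 5% chance of being triggered if the true DLT toxicity rate is 5" per cent, and gives 62% for a true rate of 30%.
- **What is counted (6.1).** "DLT is defined as any hematologic or non-hematologic AE grade ≥3 with a suspected causal relationship to Plerixafor". Seriousness is not part of the definition.
- **What must go to the monitor (7.2).** "SAEs CTCAE Grade 3 and above, and all subsequent follow-up reports will be reported to the Stanford Cancer Institute Data and Safety Monitoring Committee", whether or not related. Other adverse events are entered in source documents and case report forms.
- **What the monitor reviews (11.2).** The DSMC is the monitoring entity, and "the DSMC will regularly review serious adverse events and protocol deviations associated with the research". Its audits may look at case report forms, but need not.
- **The criterion for further studies (12.7).** The regimen is of interest if significantly more than half of the patients meet the 6-month benchmark, and the investigators "would move further to future studies should this benchmark be reached". The synopsis, 12.4 and 12.5.2 use the same kind of criterion. None mentions toxicity. Section 1.1 lists safety among the primary objectives.

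**The concern.** The trigger and the monitoring plan run on different sets of events. The trigger counts related events of grade 3 or higher. The monitor is sent serious events of grade 3 or higher. An event in the first set but not the second, such as a related grade 3 laboratory cytopenia that meets no seriousness criterion, moves the count towards its limit, yet nothing obliges anyone to send it to the DSMC. Because 12.1 names no reviewer, nothing there closes the gap.

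Two things are at stake. First, the judgement whether Phase II should go on after its own toxicity limit is reached could be made without the body appointed to monitor the trial. Section 2.4 allows Phase II patients to be enrolled and treated together, so others may be on treatment at that moment. Second, a regimen that reached a limit and was continued would still satisfy 12.7 as written, and the report could recommend further study without stating what Phase II showed about safety.

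**Working it through.** **1. The plan's own trigger probabilities.** Inputs from 12.1: at least 1 DLT in 5, 2 in 10, 2 in 15; stated trigger probabilities of 5% at a DLT rate of 5% and 62% at 30%. With true rate r and independent patients, the printed limits are not reached only if there is no DLT in the first 5 and at most one in the next 10:

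P(not reached) = (1−r)^5 × [(1−r)^10 + 10r(1−r)^9]

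- r = 0.05: 0.7738 × (0.5987 + 0.3151) = 0.707, so the trigger probability is 29.3% (stated 5%).
- r = 0.30: 0.1681 × (0.0282 + 0.1211) = 0.0251, so it is 97.5% (stated 62%).

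Neither stated figure is reproduced. If each limit is instead read as having to be exceeded (2 in 5, 3 in 10, 3 in 15):

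P(not reached) = P(0 in 5) × P(at most 2 in 10) + P(1 in 5) × P(at most 1 in 10)

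- r = 0.05: 0.7738 × 0.9885 + 0.2036 × 0.9139 = 0.951, trigger 4.9%.
- r = 0.20: 0.3277 × 0.6778 + 0.4096 × 0.3758 = 0.376, trigger 62.4%.
- r = 0.30: 0.1681 × 0.3828 + 0.3602 × 0.1493 = 0.118, trigger 88.2%.

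This reading matches the stated 5%, but 62% then belongs to a rate of 20%, not 30%. Triggering only when the count exactly equals a limit gives 28.2% and 49.4%. A search over all non-decreasing limits from 1 to 8, with looks at 5/10, 5/10/15, 5/10/20 and 5/10/15/20, found no set within 2 points of both stated figures. The limits and the probabilities contradict each other. The documents do not show which was intended.

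**2. Which events count, and which are sent.**

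| Event of grade 3 or higher | Counts to the trigger (6.1, 12.1) | Must be reported to the DSMC (7.2) |
|---|---|---|
| Related, serious | yes | yes |
| Related, not serious | yes | no |
| Unrelated, serious | no | yes |

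The second row is the gap. At the first look the limit is one event, so one such DLT in 5 patients is enough to call the review.

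**3. A second definition.** Section 10.1.2 describes the DLT outcome as the absence of cardiac arrhythmia or of grade III or IV events. It has no relatedness condition and does not mention grade 5. Section 6.1 requires suspected relatedness and has no upper grade. The two would give different counts.

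**4. How much toxicity information comes from Phase II.** Phase I has at most 9 patients over all levels (12.1). At least 3 must be treated at the starting level before escalation (2.4, 12.1), so at most 9 − 3 = 6 can be treated at the highest level. Phase II adds 20 (12.5.1). Most of the safety data on the carried-forward regimen will therefore come from the phase whose go criterion has no toxicity term.

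**The case against.** A good deal can be said for the plan.

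- **A decision is named.** Section 12.1 ties the review to whether the trial continues. A reader might infer that the trigger leads to no decision, but the text does not support that. What is missing is who makes it. A reader might also infer that it falls to the treating investigators. Section 12.1 assigns it to nobody.
- **Other safeguards exist.** A DLT ends that patient's infusion (6.1). There is on-site observation and weekly physician evaluation (6.2), weekly ECG and laboratory testing (4.0.1), interruption for electrolyte abnormalities (7.1), and rapid notice of serious related events to the drug supplier (7.2). The trigger is not the only toxicity safeguard. It is the only one that acts on the cohort's DLT count.
- **The gap may be small.** The seriousness definition in 7.1 includes important medical events, and thrombocytopenia was reported as serious in the earlier continuous-infusion study (7.1, grade not given). The DSMC may see DLTs at audit, and 7.2 has a general statement that adverse events will be reported, without a recipient. All this stands, but none of it obliges anyone to send a non-serious DLT to the DSMC.
- **The rule is not run on serious events.** A reader might calculate how rarely the limits would be reached if only serious DLTs counted. The documents do not support that: 12.1 counts all DLTs, and no serious share is given.
- **Patients 16 to 20 have no printed limit.** This is true, but after patient 20 no Phase II enrolment is left to stop, so a further limit would add little.
- **The phases have separate aims.** Sections 2.4 and 10.1 assign safety to Phase I and efficacy to Phase II, the synopsis lists safety as secondary, 12.2 tabulates DLTs, and 12.7 does not say toxicity will be disregarded. Leaving toxicity out of 12.7 is therefore a weak design choice, not a contradiction. Section 1.1, however, states the safety objective without limiting it to Phase I.

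**Conclusion.** The point holds in this form: the Phase II trigger has no named reviewer, mandatory DSMC reporting does not cover all the events that trip it, and the recommendation for further study takes no account of toxicity. The first two follow from the text and need no assumption. The third is a judgement about good design, resting on the safety objective in 1.1.

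The size of the reporting gap cannot be estimated, because the documents do not give the share of DLTs that would be non-serious. One such event among the first 5 patients is enough to expose it. The review is also likely to be needed: assuming independent patients and the printed limits, the trigger is reached in 29.3% of trials at a 5% DLT rate and 97.5% at 30%. If the limits must be exceeded, the figures are 4.9% and 88.2%. The mismatch with the stated 5% and 62% is a separate, firm error in the same section. The reporting and review wording should be changed, since the remedy is cheap and uses a committee that already exists.

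**What to change.** 1. **Sections 7.2 and 11.2:** report every DLT, serious or not, to the existing DSMC on the study case report form, with the running DLT count and the number of patients treated.
2. **Section 12.1:** name the DSMC as the body that reviews a reached limit and advises whether the trial continues.
3. **Section 12.7:** report the DLT rate at the carried-forward regimen with its exact 95% confidence interval beside the 6-month result, and have the recommendation for further study take the DSMC's toxicity conclusion into account. Align the synopsis.
4. **Same edit:** the sponsor must reconcile the limits in 12.1 with the trigger probabilities stated there, and the DLT definition in 6.1 with that in 10.1.2, so that the count sent to the DSMC has one meaning.

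The cost is protocol wording, a few more event forms and slightly more DSMC work, with no extra patients or procedures. The one real consequence is that an efficacy result no longer settles the recommendation by itself.

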12.1 Statistical Design

This is a dose-escalation study with three planned dose levels using the modified toxicity probability interval (mTPI). The mTPI method is a competitor to the usual 3+3 dose escalation scheme and to the Continuous Reevaluation Method (CRM), mTPI has the advantage of having been peer-reviewed in both the statistical literature and in the oncology literature [74]. The design has the further advantage of allowing the investigators to conduct the study without constant reference to a biostatistician (as required by the CRM approach). It also allows for planned de-escalation as in this protocol

Planned dose levels are 200 μ g/kg/d x 2 wks (continuous infusion), 100 μ g/kg/d x 4 wks, 200 μ g/kg/d x 4 wks, and 400 μ g/kg/d x 4 wks. The starting total dose will be the middle dose 200 μ g/kg/d x 4 wks.

If a DLT occurs from Day 15-28, we will treat next patient with a dose of 200 μ g/kg/d x 14 days. If a DLT occurs from day 0-14, we will treat next patients at a dose of 100 μ g/kg/d x 28 days. If a patient experiences a DLT, the infusion will be discontinued. The next patient treated at the lower dose level as dictated by the mTPI table. If an early dose limiting toxicity occurs at lowest dose level,200 μ g/kg/d x 2 wk or 100 μ g/kg x 4wks, then the protocol will be stopped at that point.

The design is based on a Bayesian calculation of the posterior probability of toxicity at each dose. The following settings have been used:

- * The target toxicity level. In this study we use the same level of 30% as in [74], which also corresponds informally to the target toxicity of the 3+3 design.
- * The precision for that target toxicity (here plus or minus 5 percentage points).
- * The maximum sample size across all dose (here 9).
- * Planned dose levels 200 μ g/kg/d x 2 wks (continuous infusion), 100 μ g/kg/d x 4 wks, 200 μ g/kg/d x 4 wks and 400 μ g/kg/d x 4 wks. The starting total dose will be the middle dose 200 μ g/kg/d x 4 wks.

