12.5.1 Analysis Population

20 additional patients will be enrolled in the Phase II component of this study for determination of efficacy.

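### The expansion-phase toxicity rule in Section 12.1 cannot have the stated 5% and 62% trigger probabilities; as printed it triggers 29% and 97.5% of the time.

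*Combined protocol and SAP*

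**What the plan says.** The rule stands near the end of Section 12.1 (Statistical Design). The schedule is: "Toxicity will be monitored in the expansion phase at each increment of 5 patients". The boundary is: "If DLT is observed in one out of the first 5 patients, or 2 of the first 10, or 2 of the first 15". On crossing it, "toxicity will be reviewed to assess whether the trial should continue". No boundary is printed for the look at 20 patients.

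Two operating characteristics follow directly: "This stopping rule has a 5% chance of being triggered if the true DLT toxicity rate is 5%, it has a 62% chance". The second is, in full, "it has a 62% chance of being triggered if the true DLT rate is 30"%.

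Section 12.5.1 gives the size of the expansion: "20 additional patients will be enrolled in the Phase II component of this study for determination of efficacy". Section 12.1 also sets the Phase I target toxicity at 30% and defines the maximum tolerated dose as the level closest to that target. Section 10.1.1 carries the dose so determined into the 20-patient expansion.

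**The concern.** A boundary that is crossed by a single DLT among five patients is a sensitive one. Even at a true rate of 5%, about one group of five in four or five will contain a DLT, so a 5% overall trigger probability looked too low on sight.

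This is the only numerical cohort threshold for toxicity in the expansion, and whoever conducts the review will interpret a flag in light of the stated properties. Someone who believes that a safe dose is flagged only 5% of the time will read too much into a flag. The operational question is also unsettled: does one DLT in the first five patients call for a review? The printed boundary says yes, but the stated 5% belongs to a looser boundary under which it would not.

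Such an event is realistic. Section 6.1 counts any grade 3 or higher event with suspected relation to plerixafor, Section 7.1 treats possibly related events as related, and the infusion starts during chemoradiation.

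**Working it through.** **Inputs, all from Section 12.1.** Looks after 5, 10 and 15 expansion patients; trigger at a cumulative count of at least 1, at least 2 and at least 2 DLTs respectively; stated trigger probabilities of 0.05 at a true DLT rate p = 0.05 and 0.62 at p = 0.30. Patients are taken as independent with a common rate p.

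**Step 1: the first look alone.** P(at least 1 DLT in 5) = 1 − (1 − p)^5.

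- p = 0.05: 1 − 0.95^5 = 1 − 0.7738 = 0.226, against a stated overall 0.05.
- p = 0.30: 1 − 0.70^5 = 1 − 0.1681 = 0.832, against a stated overall 0.62.

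Further looks cannot lower the chance of ever triggering, so both stated figures are already ruled out.

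**Step 2: all three looks.** Avoiding a trigger requires no DLT in the first 5 and at most 1 in the first 15. The condition at 10 is then met automatically. Hence

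P(trigger) = 1 − (1 − p)^5 × P(Bin(10, p) ≤ 1).

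- p = 0.05: 1 − 0.7738 × 0.9139 = 0.293.
- p = 0.30: 1 − 0.1681 × 0.1493 = 0.975.

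An exact recursion gives the same values (0.2929 and 0.9749), and a simulation of 200,000 trials gives 0.292 and 0.974.

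**Step 3: other readings of the rule.**

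| Reading | p = 5% | p = 10% | p = 20% | p = 30% |
|---|---|---|---|---|
| Stated in Section 12.1 | 5% | – | – | 62% |
| As printed (≥1/5, ≥2/10, ≥2/15) | 29.3% | 56.5% | 87.7% | 97.5% |
| Exactly 1, exactly 2, exactly 2 | 28.2% | 50.3% | 62.1% | 49.4% |
| Separate blocks of 5 (≥1, ≥2, ≥2) | 26.1% | – | – | 95.3% |
| More than 1, 2, 2 (≥2/5, ≥3/10, ≥3/15) | 4.9% | 21.0% | 62.4% | 88.2% |

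No reading gives 5% at a 5% rate together with 62% at a 30% rate. A search over non-decreasing boundaries with two, three or four looks, and over single-look rules, found none within 2 percentage points of both.

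**Step 4: the nearest match.** The last row can be checked by hand. Avoiding a trigger requires at most 1 DLT in 5 and at most 2 in 15, so

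P(trigger) = 1 − [P(X₅ = 0) × P(Bin(10, p) ≤ 2) + P(X₅ = 1) × P(Bin(10, p) ≤ 1)].

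- p = 0.05: 1 − (0.7738 × 0.9885 + 0.2036 × 0.9139) = 0.049.
- p = 0.20: 1 − (0.3277 × 0.6778 + 0.4096 × 0.3758) = 0.624.

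The stated 5% and 62% therefore fit a stricter-inequality rule at true rates of 5% and 20%. At the printed 30% that rule gives 88.2%, so the text would still be wrong.

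**The case against.** The strongest reply concerns consequences, since the arithmetic is not in dispute. Crossing the boundary leads to a review, not an automatic halt. The printed boundary is stricter than its stated properties, so following it as written gives more oversight, not less. Other safeguards run in parallel: the infusion stops for any patient with a DLT (Sections 4.2 and 6.1), and the DSMC receives and reviews serious events (Sections 7.2 and 11.2). All of that stands. The figures here are flag probabilities, and no failure to detect toxicity has been shown. But protection is greater only if the printed boundary is the intended one, which the contradiction leaves open.

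A second reply is that the dose taken forward need not have a 30% DLT rate. Section 2.4 makes the expansion conditional on reaching the top dose without significant toxicity, and Section 12.4.1 foresees that no level may reach 30%. A stricter tolerance in the expansion than in dose finding can also be a deliberate choice. This is fair, and it makes the tension with the Phase I target a separate design question. It does not rescue the stated 62%, and even at a true rate of 20% the printed rule flags 87.7% of the time.

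Third, the origin of the stated pair is not established. The match to a more-than rule at 5% and 20% comes from a search, and minor variants fit as well: dropping the look at 10 patients, which changes nothing, or adding a high threshold at 20. That the wording lost a more-than and 20% became 30% is an inference the plan does not confirm. The correction does not depend on it.

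**Conclusion.** The concern holds. For the rule as printed, the trigger probability is 29.3% at a true DLT rate of 5%, not 5%, and 97.5% at 30%, not 62%. The false-alarm rate is understated about sixfold (29.3/5 ≈ 5.9).

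This assumes independent patients with a common DLT rate, cumulative counts among expansion patients only, and a trigger when the count reaches or exceeds the printed number. The other readings tried do not restore the stated pair, so at least one printed element (the boundary, the rates or the probabilities) is wrong under each of them.

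The harm is a misdescribed safety rule and doubt about which boundary governs.

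**What to change.** In Section 12.1, print one boundary together with its own probabilities. Which boundary applies is for the sponsor to decide.

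- If the printed boundary is intended, write it as at least 1 of 5, at least 2 of 10 and at least 2 of 15. Replace the two figures with 29% at a 5% DLT rate, 88% at 20% and 97.5% at 30%.
- If the looser boundary is intended, write it as more than 1 of 5, more than 2 of 10 and more than 2 of 15 (2, 3 and 3 or more DLTs). Give 4.9% at 5%, 62% at 20% and 88% at 30%.

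In either case, describe the figures as probabilities of prompting a review. As a separate and desirable addition, say in one sentence how the rule relates to the 30% target used to choose the dose, since either version flags a true 30% rate in most trials.

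The cost is a wording amendment, with no extra patients or procedures. If the printed boundary is kept, the sponsor must accept a less favourable stated false-alarm rate.
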